**Table 4: Enrollment Visit Procedures**

Enrollment Visit Procedures (Day 0)*		
Administrative Tasks		
 
• Confirm study ICD is completed and signed and dated by both parent/guardian and study staff who completed the consenting process
 
• Complete eligibility determination and confirmation
 
• Complete paper-based eligibility checklist
 
• Obtain release of medical records as required per HIPAA
 

Clinical Tasks		
 
• Obtain interim history from parent/guardian
 
• Perform physical exam: 
 
◦ Complete physical exam if deferred at screening, OR
 
◦ Focused physical exam if physical completed at screening
 
 
 
• Address any concerns
 
• Document findings
 
• Confirm eligibility
 

Laboratory Tasks	Blood	
If insufficient volume obtained at screening, collect blood for:
 
 
• Pre-inoculation RSV antibody titer
 

	Nasosorption SAM Strip and/or Nasal Wash	
Collect nasosorption strip for:
 
 
• RSV antibody assays
 
 
Note: The nasosorption must be performed prior to the nasal wash.
 
The nasal wash must be obtained prior to administering the study product.
 
Collect nasal wash for:
 
 
• RSV antibody assays
 
• RSV viral detection and quantification
 

Study Product Administration		
 
• Administer study product and maintain participant in a supine position for 1 minute
 
• Observe for approximately 30 minutes after inoculation to evaluate for immediate hypersensitivity reactions
 

Follow-up Preparation		
 
• Provide the following: temperature card with explanation, temporal and rectal thermometers with instructions for use, illness criteria explanation, and study personnel contact information
 
• Schedule non-visit day contact and schedule next in-person visit
 
• Offer parent/guardian safety seat education materials, and a safety seat educator appointment
 
• Offer parent lactation services by a certified lactation counselor, if appropriate
 

\*Within same calendar year as screening for RSV-seropositive participants, and no more than 42 days from screening for RSV-seronegative participants

Following the inoculation day visit, the parent/guardian will record the infant/child's temperatures and signs of illness on the temperature card and provide these to study personnel during an in-person visit or non-visit day contact. New rectal thermometers will be given and temporal artery thermometers will be provided to parent/guardian for use during the study. For temperature measurements, parent/guardian will be instructed to use the study-provided temporal artery thermometer to screen for elevated temporal artery temperatures. This device is used to minimize the number of rectal temperature measurements and has been shown to be an effective screening tool for rectal fever (37). The parent/guardian will measure temporal artery temperatures following the manufacturer's directions. If any temporal artery temperature is  $\geq 100.0^{\circ}\text{F}$ , parent/guardian will be asked to measure a rectal temperature within 20 minutes (37). For study-specific management and grading of temperatures, see Section 8, Table 22.

## 6.4.2 Enrollment in the Second Season of RSV Surveillance (Group 2 Only)

Participation in RSV surveillance for a second season will require completion of an additional consent document by the parent or guardian. The consent document for this optional portion of the study may be done at the pre-RSV second seasonal surveillance visit or at a separate visit prior to the pre-RSV second seasonal surveillance visit.

## 6.5 STUDY PHASES

Refer to [Figures 1](#) and [2](#) for timelines of study visits. The Acute Phase begins with inoculation and ends at midnight on the 10th day after inoculation for RSV-seropositive participants, and at midnight on the 28th day after inoculation for RSV-seronegative participants. During the Acute Phase of the study, a study healthcare professional will be available by telephone 24 hours a day for consultation with parent/guardian regarding any illnesses that may occur.

Study personnel will have daily contact with RSV-seropositive participants' parents/guardians for the first 10 days after inoculation, and for the RSV-seronegative participants during the first 28 days after inoculation. This 28-day period is consistent with the duration of shedding of live-attenuated respiratory virus vaccines in RSV-seronegative participants ([28](#), [37-39](#)).

On non-visit days, study staff will contact the parent/guardian and will record the parent/guardian-provided temperatures and signs of illness. Participants with illness may have additional visits to assess the illness (Section [6.8](#), Illness Visit).

### 6.5.1 RSV-Seropositive Children (Group 1)

#### 6.5.1.1 Acute Phase: In-person Study Visit Days

An in-person study visit and clinical assessment performed by a healthcare professional will be completed during visits on days 3, 4, 5, 6, 7, and 10 after inoculation, with a visit window of  $\pm 1$  day. If an in-person visit is moved by  $\pm 1$  day, then the non-visit day contact will be completed in place of the original interim visit date.

**Table 5: Acute Phase In-Person Visit Procedures – RSV-Seropositive Children**  
**Days 3, 4, 5, 6, 7 and 10 In-person Visit Procedures (each visit  $\pm 1$  days)**

Clinical Tasks		

• Obtain and document from parent/guardian the participant's previous days' interim history including:

▪ medications and/or immunizations

▪ signs and symptoms of illness

▪ highest temperature reading, indicate temperature method

• Perform focused clinical examination

• Address any concerns

• Review safety data

• Document findings

Laboratory Tasks	Nasal wash	Collect nasal wash for: 

• RSV viral detection and quantification

Follow-up Preparation		

• Schedule non-visit day contact and follow-up, in-person visits Day 10 only:

• Review SAE criteria with participants and how to contact study personnel during Post-Acute Phase

During an Acute Phase study visit, if the participant is diagnosed with or suspected of having URI, LRI, otitis media or fever (as defined in [Appendix IV](#)), testing of the nasal wash specimen for adventitious agents will be performed as described in the MOP.

### 6.5.1.2 Acute Phase: Non-Visit Study Day Contacts

In the 10 days following inoculation, parental contact will be made on days that an in-person visit is not completed: days 1, 2, 8, and 9 (each visit  $\pm$  1 day). On non-visit days, study staff will contact the parent/guardian and will record the parent/guardian-provided temperatures and signs of illness. Participants with illness may have additional visits to assess the severity of the illness (Section [6.8](#)).

**Table 6: Acute Phase Non-Visit Contact Procedures – RSV-Seropositive Children**

Days 1, 2, 8, and 9 Contact Procedures (each visit <math>\pm</math> 1 day)	
Clinical Tasks	
 
• Obtain and document from parent/guardian the participant's interim history from previous days, including:           
 
▪ medications and/or immunizations
 
▪ signs and symptoms of illness
 
▪ highest temperature reading, indicate temperature method
 
 
 
• Address any concerns
 
• Review safety data
 
• Document findings
 

Follow-up Preparation	
 
• Schedule an illness appointment if necessary
 

### 6.5.1.3 Study Day 11

There will be a non-visit contact on Day 11 to obtain interim history through midnight on the 10th day following inoculation. If the Day 10 Visit takes place on Day 11, it is not necessary to have an additional contact with the family on Day 11.

**Table 7: Day 11 Non-Visit Procedures – RSV-Seropositive Children**

Day 11 Non-Visit Procedures	
Clinical Tasks	
 
• Obtain and document from parent/guardian the participant's previous days' interim history including:           
 
▪ medications and/or immunizations
 
▪ signs and symptoms of illness
 
▪ highest temperature reading, indicate temperature method
 
 
 
• Address any concerns
 
• Review safety data
 
• Document findings
 

Follow-up Preparation	
 
• Review SAE criteria with participants and how to contact study personnel during Post-Acute Phase
 

#### 6.5.1.4 Post-Acute Phase

The Post-Acute Phase begins on the 11th day after inoculation and ends on the 28th day after inoculation. During the Post-Acute Phase, parent/guardian will be instructed to monitor for and contact the study staff if their child has symptoms that are suggestive of a SAE. If the parent reports an SAE that may meet the study pause or stop criteria (Section 8.3), then an Illness Visit will be scheduled (Section 6.8).

#### 6.5.1.5 Study Day 28 Visit

The Day 28 Visit should be conducted between 28 and 35 days following inoculation. Because the Post-Acute Phase ends as the 28th day following inoculation, only events through that time should be evaluated as having occurred during the Post-Acute Phase.

**Table 8: Day 28 Visit Procedures – RSV-Seropositive Children**

Day 28 Visit (+7 Days)	
Administrative Tasks	

Provide study compensation

Clinical Tasks	

Obtain and document from parent/guardian the participant's interim history from midnight of the 10th day through the 28th day following inoculation, including:

visits to medical provider/hospitalizations

medications and/or immunizations

signs and symptoms of illness meeting SAE criteria

Address any concerns

Review safety data

Document findings

Laboratory Tasks	Collect blood for: 

Serum antibodies to RSV

	Collect nasosorption strip for: 

RSV antibody assays

 
Note: The nasosorption must be performed prior to the nasal wash.
 
The nasal wash must be obtained prior to administering the study product.
 Collect nasal wash for: 

RSV antibody assays

#### 6.5.2 RSV-Seronegative Infants and Children

##### 6.5.2.1 Acute Phase: In-person Study Visit Days

An in-person study visit and clinical assessment performed by a healthcare professional will be completed during visits on Study Days 3, 5, 7, 10, 12, 14, 17 and 28 after inoculation with a visit window of  $\pm 1$  day. If an in-person visit is moved by  $\pm 1$  day, then the non-visit day contact is completed in place of the original interim visit date.

**Table 9: Acute Phase In-Person Visit Procedures – RSV-Seronegative Children****Days 3, 5, 7, 10, 12, 14, 17, and 28 In-person Visit Procedures (each visit  $\pm$  1 days)**

Clinical Tasks		
 
• Obtain and document from parent/guardian the participant's previous days' interim history including:           
 
▪ medications and/or immunizations
 
▪ signs and symptoms of illness
 
▪ highest temperature reading, indicate temperature method
 
 
 
• Perform focused clinical examination
 
• Address any concerns
 
• Review safety data
 
• Document findings
 

Laboratory Tasks Nasal Wash and/or Nasosorption SAM Strip		
Collect nasal wash for:
 
 
• RSV viral detection and quantification
 
 
Day 28 only: Collect nasal wash for:
 
 
• RSV antibody assays
 
• RSV viral detection and quantification
 
 
Day 28 only: Collect nasosorption strip for:
 
 
• RSV antibody assays
 
 
Note: The nasosorption must be performed prior to the nasal wash.

Follow-up Preparation		
 
• Schedule non-visit day contact and follow-up, in-person visits
 
 
Day 28 only:
 
 
• Review SAE criteria with participants and how to contact study personnel during Post-Acute Phase
 

### 6.5.2.2 Acute Phase: Non-Visit Study Day Contacts

In the 28 days following inoculation, parental contact will be made on days that an in-person visit is not completed: days 1, 2, 4, 6, 8, 9, 11, 13, 15, 16, and 18–27 (each visit  $\pm$  1 day). On non-visit days, study staff will contact the parent/guardian and will record the parent/guardian-provided temperatures and signs of illness. Participants with illness may have additional visits to assess the severity of the illness (Section 6.8).

**Table 10: Acute Phase Non-Visit Contact Procedures – RSV-Seronegative Children****Days 1, 2, 4, 6, 8, 9, 11, 13, 15, 16, 18 , 19, 20, 21, 22, 23, 24, 25, 26 and 27 Contact Procedures (each visit  $\pm$  1 day)**

Clinical Tasks		
 
• Obtain and document from parent/guardian the participant's previous days' interim history including:           
 
▪ medications and/or immunizations
 
▪ signs and symptoms of illness
 
▪ highest temperature reading, indicate temperature method
 
 
 
• Address any concerns
 
• Review safety data
 
• Document findings
 

Follow-up Preparation		
 
• Schedule an illness appointment if necessary
 

### 6.5.2.3 Study Day 29

There will be a non-visit contact on Day 29 to obtain interim history through midnight on the 28th day following inoculation. If the Day 28 Visit takes place on Day 29, it is not necessary to have an additional contact with the family on Day 29.

**Table 11: Day 29 Non-Visit Procedures – RSV-Seronegative Children**

Day 29 Non-Visit Procedures	
Clinical Tasks	

• Obtain and document from parent/guardian the participant's previous days' interim history including:

▪ medications and/or immunizations

▪ signs and symptoms of illness

▪ highest temperature reading, indicate temperature method

• Address any concerns

• Review safety data

• Document findings

Follow-up Preparation	

• Review SAE criteria with participants and how to contact study personnel during Post-Acute Phase

### 6.5.2.4 Post-Acute Phase

The Post-Acute Phase begins on the 29th day after inoculation and ends on the 56th day after inoculation. During the Post-Acute Phase, parent/guardian will be instructed to monitor for and contact the study staff if their infant or child has symptoms that are suggestive of a SAE. If the parent reports an SAE that may meet the study pause or stop criteria (Section 8.3) then schedule an Illness Visit (Section 6.8).

### 6.5.2.5 Study Day 56 Visit

The Day 56 Visit should be conducted between 56 and 63 days following inoculation. Because the Post-Acute Phase ends on the 56th day following inoculation, only events through that time should be evaluated as having occurred during the Post-Acute Phase.

**Table 12: Day 56 Visit Procedures – RSV-Seronegative Children**

Day 56 Visit (+7 Days)	
Administrative Tasks	
 
• Provide first study compensation payment
 

Clinical Tasks	
 
• Obtain and document from parent/guardian the participant's interim history from midnight of the 28th day through the 56th day following inoculation, including: 
 
▪ visits to medical provider/hospitalizations
 
▪ medications and/or immunizations
 
▪ signs and symptoms of illness meeting SAE criteria
 
 
 
• Address any concerns
 
• Review safety data
 
• Document findings
 

Laboratory Tasks	Blood Collect blood for: 
 
• Serum antibodies to RSV
 

	Nasosorption SAM Strip and/or Nasal Wash Collect nasosorption strip for: 
 
• RSV antibody assays
 
 
Note: The nasosorption must be performed prior to the nasal wash.
 
Collect nasal wash for:
 
• RSV antibody assays
 

Follow-up Preparation	
Follow-up depends on when, during the calendar year, the Day 56 Visit is conducted. If Day 56 Visit is conducted:
 
 
• Prior to October 1 
 
▪ schedule Pre-RSV Season Visit (Section 6.6.1)
 
 
 
• On or after October 1 
 
▪ Day 56 Visit will also be the Pre-RSV Season Visit
 
▪ Review plans for weekly contact during the RSV Season Surveillance Period (Section 6.6.2)
 
 
 

### 6.5.2.6 Period after Day 56 through October 31st

During this period, contact with the participant is not required except for the Pre-RSV Season Study Visit described in Section 6.6.1. No clinical data will be recorded on CRFs or reported under this protocol except for data as outlined in Section 7.2.

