**Table 13: Pre-RSV Season Surveillance Study Visit Procedures**

Pre-RSV Season Study Visit (October 1 through October 31 of enrollment year)	
Clinical Tasks	
 
• Document findings related to study procedure
 

Laboratory Tasks	
Collect blood for:
 
 
• Serum antibodies to RSV
 

Nasosorption SAM Strip and/or Nasal Wash	
Collect nasosorption strip for:
 
 
• RSV antibody assays
 
• Note: The nasosorption must be performed prior to the nasal wash.
 
 
The nasal wash must be obtained prior to administering the study product.
 
Collect nasal wash for:
 
 
• RSV antibody assays
 

Follow-up Preparation	
 
• Review plans for weekly contact during the RSV Season Surveillance Period (see Section 6.6.2)
 

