### **7.1.5 Sponsor Reporting**

A SUSAR is a suspected adverse reaction that is both serious and unexpected, as defined in 21 CFR 312.32. SUSARs will be reported to the FDA and all participating investigators as IND Safety Reports. The Regulatory Sponsor will also submit a brief report of the progress of the investigation to the FDA on an annual basis as defined in 21 CFR 312.33.

Following notification from the PI, OCRPRO, as the IND Sponsor, will report all SAEs to the FDA within the required timelines. Fatal and life-threatening events will be reported within 7 calendar days of the sponsor's awareness and all other SAEs will be reported within 15 calendar days of the sponsor's awareness.

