**Table 20: AE CRF Recording Requirements for RSV-Seronegative Subjects**

Study Phase at the Time of Event Onset	Calendar Date	AEs to Record on CRFs	Concomitant Medications to Record on CRFs
Day 0 through midnight of 28 th day following inoculation (Acute Phase)	ANY	
 
• All SAEs
 
• All solicited AEs that meet Appendix IV criteria
 
• All unsolicited AEs (Grades 1 to 4), with the exception of the following conditions if not treated with prescription medication or non-prescription medications with antipyretic properties: diaper rashes, teething pain, and spitting up
 
	
Record these medications on the CRFs regardless of whether the related event is recorded on the CRFs:
 
 
• All cough and cold remedies including decongestants, cough suppressants, expectorants
 
• All nasal sprays (except saline spray)
 
• All antihistamines
 
• All antipyretics
 
• All prescription medications
 
 
For SAEs and LRIs:
 
 
• All medications related to the recorded event
 

From the 29 th day after inoculation to the 56 th day after inoculation (Post-Acute Phase)	ANY	
 
• All SAEs
 
	
 
• All medications related to the recorded event
 

From Day 56 Visit through start of RSV Season Surveillance Period	Up to October 31 in year of inoculation	
 
• Grade <math>\geq 3</math> AEs or SAEs that is deemed related to Pre-RSV Season Study Visit procedures
 
	
 
• All medications related to the recorded event
 

RSV First and Second Season Surveillance Periods	November 1 to March 31	
 
• Fevers, LRIs, URIs, and/or otitis media that are medically attended
 
• All SAEs
 
 
Note: These events do not need to meet the Appendix IV criteria
	
For SAEs and LRIs (all grades):
 
 
• All medications related to the recorded event
 
 
Medications related to recorded medically attended illness should be documented in source notes

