Post-RSV Season	Ideally April 1 to April 30; allowable through Sept 30th in the year after the inoculation	
 
• Grade <math>\geq 3</math> AEs or SAEs that are deemed related to Post-RSV Season Study Visit procedures
 
	
 
• All medications related to the recorded event
 

Throughout study	ANY	
 
• Unresolved AEs or SAEs with onset from Day 0 to midnight on the 28th day after inoculation
 
• Unresolved SAEs with onset prior to the 56th day following inoculation
 
• Unresolved SAEs with onset during RSV Surveillance Period or related to the Pre- or Post-RSV Season Study Visit
 
	
 
• All medications related to the recorded event
 

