### 7.3 SERIOUS ADVERSE EVENT REPORTING

All SAEs will be reviewed by a study physician, recorded on the Safety Expedited Report Form (SERF) and followed through to resolution. SAEs that have not resolved by the end of the follow-up period are followed until final outcome is known. If it is not possible to obtain a final outcome for an SAE (e.g., the subject is lost to follow-up), the reason a final outcome could not be obtained will be recorded by the investigator on the AE CRF and the SERF. In addition to the SAE Reporting Category identified below, other AEs that must be reported in an expedited manner are LRIs as defined in Appendix IV if they occur during study days 0 to 10 in groups 1 and study days 0 to 28 in group 2.

Deaths and immediately life-threatening SAEs will be reported within 1 business day after the site becomes aware of the event. All other SAEs will be reported within 3 business days of site awareness. SAEs will be reported either by fax or e-mail to all of the following:

- Sponsor: Office of Clinical Research Policy and Regulatory Operations, NIAID, NIH: Clinical Safety Office (CSO): [contact], [contact], [[contact]](mailto:[contact])
- DSMB Executive Secretary: [contact], [contact], [[contact]](mailto:[contact])
- LID, NIAID: [name], NIAID/NIH, [contact], [contact], Email: [[contact]](mailto:[contact])

SAEs will also be reported to WIRB (contact information below) based on its reporting requirements:

- Western Institutional Review Board (WIRB), [name], [contact]

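### In Group 2, a new product-related SAE starting from Day 57 to October 31, or after March 31, has no CRF row in Table 20, and Section 6.5.2.6 contradicts Section 7.3 on reporting it in the first window

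*Combined protocol and SAP*

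**What the plan says.** Group 2 children stay on study until the post-season visit (Protocol Summary, Study Duration). Table 20 collects all SAEs through Day 56 and again from November 1 to March 31. Between and after those periods it narrows:

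- From the Day 56 Visit to October 31 it lists only Grade 3 or higher "AEs or SAEs that is deemed related to Pre-RSV Season Study Visit procedures".
- Post-season it lists only Grade 3 or higher "AEs or SAEs that are deemed related to Post-RSV Season Study Visit procedures".
- The Throughout study row carries forward events that began in a covered period or relate to a season visit, for example "Unresolved SAEs with onset prior to the 56 th day following inoculation".

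Section 6.5.2.6 governs the first of these periods. On contact it says: "During this period, contact with the participant is not required except for the Pre-RSV Season Study Visit described in Section 6.6.1". On data it says: "No clinical data will be recorded on CRFs or reported under this protocol except for data as outlined in Section 7.2".

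The reporting sections have no such limit. Section 7.3 says: "All SAEs will be reviewed by a study physician, recorded on the Safety Expedited Report Form (SERF) and followed through to resolution". Its clock runs from site awareness: one business day for deaths and immediately life-threatening events, three for other SAEs. Section 7.1.5 has the sponsor pass all SAEs to the FDA once the investigator has notified it, and adds: "SUSARs will be reported to the FDA and all participating investigators as IND Safety Reports". Section 9.4.2 sends all SAEs to the DSMB.

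**The concern.** This is a live vaccine given to humans for the first time (Section 1.2.3), here to children from 6 months of age. A late SAE that the investigator attributes to the product is rare, but it is an event that the sponsor and the DSMB would want to know about. As written, such an event cannot enter the study database in either window. In the first window, a site has one section telling it not to report and another telling it to report. The first window also lies inside the April to October enrolment period, when other children may still be receiving the product. The length of SAE coverage on the CRF depends on the calendar date of inoculation and not on time since the dose.

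**Working it through.** The plan gives no figure to reproduce. The check sets the sections side by side and then counts days.

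**1. Where a new product-related SAE would be recorded and reported (Group 2)**

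| Onset | CRF row in Table 20 | Reporting text |
|---|---|---|
| Day 0 to Day 56 | Yes, all SAEs | 7.3, 7.1.5, 9.4.2: all SAEs |
| Day 57 to October 31 | No, visit-procedure events only | 6.5.2.6 excludes it; 7.3, 7.1.5 and 9.4.2 include it |
| November 1 to March 31 | Yes, all SAEs | 7.3, 7.1.5, 9.4.2: all SAEs |
| April 1 to post-season visit | No, visit-procedure events only | 7.3, 7.1.5, 9.4.2: all SAEs; nothing bars reporting |

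The Throughout study row does not help, because it only continues events already captured.

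Section 7.3 does not settle the second line of the table. Section 8.1.2 defines an SAE as an AE that meets a seriousness criterion, and its death criterion is limited to the protocol-defined surveillance period. Section 7.2 ties AEs to the protocol's reporting periods. A site could read a Day 60 event as outside Section 7.3 altogether. Sponsor reporting under Section 7.1.5 starts from the investigator's notification, so that reading would stop the chain at the site.

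**2. Whether anyone would ask**

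- Section 6.5.2.4 instructs parents to report possible SAEs for the Post-Acute Phase, which ends on Day 56. The Day 56 Visit history (Table 12) also stops there.
- The clinical task at the pre-season visit is "Document findings related to study procedure" (Table 13). The post-season visit has the equivalent task (Table 15).
- Table 32 marks interim history for weekly contacts, Illness Visits and early discontinuation, but not for the pre- or post-season visit.

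**3. Length of the gaps**

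Inputs: enrolment April 1 to October 31; surveillance November 1 to March 31; post-season visit targeted for April 1-30 and allowed to September 30 (Table 14). Days are counted inclusively, assuming no February 29.

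- First gap = days from (inoculation + 57) to October 31, or zero if that date falls later. April 1 + 57 days = May 28. May 28 to October 31 = 4 + 30 + 31 + 31 + 30 + 31 = **157 days**. September 4 + 57 days = October 31, which gives 1 day. From September 5 the gap is zero.
- Enrolment dates with some first gap: April 1 to September 4 = 157 of 214 (73%).
- Second gap = April 1 to the post-season visit: up to **30 days** at the target and up to **183 days** at the latest date.
- Share of time on study = (first gap + second gap) / (inoculation to post-season visit):

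| Inoculated | First gap | Visit April 30 | Visit September 30 |
|---|---|---|---|
| April 1 | 157 | (157+30)/395 = 47% | (157+183)/548 = 62% |
| July 1 | 66 | (66+30)/304 = 32% | (66+183)/457 = 54% |
| October 31 | 0 | 30/182 = 16% | 183/335 = 55% |

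Group 2 opens only after Group 1 has been assessed for LRI through Day 28. If both groups enrol in the same year, the earliest Group 2 date is about April 29 (April 1 + 28 days). The first gap is then June 25 to October 31 = 6 + 31 + 31 + 30 + 31 = 129 days, and the shares become (129+30)/367 = 43% and (129+183)/520 = 60%. The 157-day maximum needs Group 2 to be open on April 1, which means a later year than Group 1.

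The optional second season is left out of these counts.

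**The case against.** The strongest reply is that the CRF gap is deliberate and safety reporting does not depend on it. Section 7.2 acknowledges a period with no AE recording on CRFs. The windows fit a single-dose vaccine: Section 6.5 puts shedding within 28 days, the primary SAE objective and the SAE pausing rule end at Day 56, and full SAE capture returns for the RSV season. Sections 7.3, 7.1.5 and 9.4.2 cover all SAEs without an end date, and Section 7.4 is a further route for unexpected, related events that raise risk. The safety communication plan mentioned in Section 7.1.2 may say more, but it is not available here.

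Much of this stands, and it rules out several stronger readings that a reader might infer:

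- *That late vaccine-related SAEs go unreported.* The documents contradict each other on this for the first window. A site that withheld such an event under Section 6.5.2.6 would breach Section 7.3.
- *That reporting is barred after March 31.* Section 6.5.2.6 ends at October 31, and no other text bars it.
- *That a death or hospitalisation could not come to light.* Parents may volunteer events, a missed visit would prompt questions, and weekly contacts with interim history begin on November 1. What is missing is a procedure that asks about the gap.
- *That 62% is typical.* It needs both an April 1 inoculation and a September 30 visit.

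The reply does not resolve the conflict between Sections 6.5.2.6 and 7.3. It also gives no reason to leave product-related SAEs out of the database while the child is on study.

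**Conclusion.** The point holds in this form. Table 20 has no CRF row for a new product-related SAE in either window. In the first window, Section 6.5.2.6 contradicts Sections 7.3, 7.1.5 and 9.4.2 on whether it is reported. Detection in both windows depends on someone volunteering the information.

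The first gap ranges from zero to 157 days by inoculation date, and the second runs up to 30 days at the target visit date or 183 at the latest. The primary Day 0-56 SAE endpoint and its analysis do not change. The sizes rest on calendar arithmetic and on when Group 2 and the post-season visits actually fall. They measure uncovered time and do not estimate how many events would be missed. The sponsor should correct this; it is a safety-capture defect and does not threaten the trial's conclusions.

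**What to change.** 1. In the Throughout study row of Table 20, and in the exception in Section 6.5.2.6, state that any death, and any SAE the investigator considers related to study product, is recorded on the CRF and the SERF and reported under Section 7.3, whatever its onset date while the child is on study.
2. At the existing pre- and post-season visits (Tables 13, 15 and 32), add one interim-history question on deaths, hospitalisations and other SAEs since the last contact. When the Day 56 Visit doubles as the pre-season visit, or the pre-season visit falls before October 31, let the interim history at the first weekly contact reach back to that visit.
3. Leave the primary Day 0-56 SAE window as it is.

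The cost is one table entry, one sentence and one question, with no new visits or samples. The downside is a few more SAE forms.
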